### 3. Compare surgical options as a function of patellofemoral anatomy

Variations in patellar tracking and contact pressure will be compared between MPFL reconstruction and tuberosity medialization. Techniques to alter trochlear dysplasia and tuberosity lateralization will also be developed and applied to the models. Simulations performed while varying anatomy will establish ranges over which each surgical option limits patellar maltracking without elevating contact pressures.

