## Approach

### Aim 1: Simulation of instability

Models for dynamic simulation of knee function will be developed to represent 12 knees with recurrent patellar instability. Simulation of motion will be performed using multibody dynamics software. Springs will be used to represent the anterior and posterior cruciate ligaments, the medial and lateral collateral ligaments, the posterior capsule, the patellar tendon, and the lateral and medial retinaculum. Quadriceps muscle forces will be applied to the patella through springs representing the quadriceps tendon. Medial and lateral hamstrings forces will apply one-third of the quadriceps force to the tibia along the long axis of the femur.

Solid bodies representing the femur, patella, and tibia will include the corresponding cartilage for each bone. Cartilage contact at the tibiofemoral and patellofemoral articulations will be governed by simplified Hertzian contact. Patellofemoral and tibiofemoral kinematics and detailed pressure maps will be characterized during post-processing by applying rigid body translations and rotations exported from the simulation to the bone models, reproducing the simulated joint motion. At flexion angles with the patella engaged with the trochlear groove, starting at 15°, muscle and ligament force vectors exported from the simulation will be applied to the patella. Overlap between cartilage on the femur and patella will be combined with the elastic modulus and Poisson's ratio of the cartilage to determine reaction forces on elements on the surface of the patella based on linear elastic theory, referred to as the discrete element analysis technique. The position of the patella within the trochlear groove will be iteratively modified until the joint compression, lateral force and tilt moment are balanced, producing a pressure pattern based on the applied force and area for each element. Tibiofemoral and patellofemoral kinematics will be quantified from the motion of local coordinate axes embedded in each bone based on anatomical landmarks using the floating axis coordinate system.

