High resolution MRI scans of subjects with patellar instability are currently available for 7 subjects from a previous study (3T scanner, extremity coil, proton density-weighted images, sagittal plane, 0.3 mm in plane resolution, 1.5 mm slice thickness). Models will be reconstructed from these scans, allowing representation of cartilage surfaces and attachment points for the ligaments, patellar tendon, and quadriceps tendon. Five additional subjects scheduled for surgical stabilization for recurrent patellar instability will be recruited to meet the proposed sample size of 12 models.

The 5 recruited subjects will participate in pre-operative computational reconstruction of in vivo knee function with closed chain loading conditions. The technique uses high resolution MRI scans to create computational models of the femur, patella and tibia, as well as the cartilage. Low resolution scans are acquired during isometric quadriceps contraction with the knee positioned at multiple flexion angles, with the aid of a MRI-compatible loading frame that applies a spring-loaded force of 60 N to 85 N along the axis of the body at the foot. Shape matching algorithms align models of the bones from the high resolution images, with attached cartilage, to bones reconstructed from lower resolution scans with the knee flexed.

Models of each knee will be used to simulate the in vivo function. The muscle forces will be ramped up until the

reaction force at the foot reaches the spring force applied in vivo. A direct comparison of tibiofemoral and patellofemoral kinematics and contact pressures between computational and in vivo data will be performed. The accuracy of computational simulation will be reported in terms of root mean square errors between the computational and in vivo data, along with correlation coefficients evaluating the accuracy of variations in output related to changing the flexion angle and between knees. Once the pre-operative models are validated by comparison to the output from reconstruction of in vivo function, they will be used to represent a dynamic squatting

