### **Aim 2: Simulation of surgical stabilization**

Accuracy of the post-operative models will be assessed in the same manner as the pre-operative models. The newly enrolled subjects will be treated surgically, with the procedure performed based solely on clinical evaluation, and will participate in post-operative computational reconstruction of in vivo knee function. All models will be modified to represent the post-operative condition based on the imaging data and the surgical notes. The post-operative models will be used to simulate function and compare kinematics and contact pressure data to the data determined from the subjects.

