### **Aim 3: Compare surgical options**

The simulation models will be used to represent two primary surgical options: reconstruction of the medial patellofemoral ligament and realignment of the tibial tuberosity, while also varying parameters related to knee anatomy. The kinematics and pressure output from all the simulated surgical variations will be compared between the 12 models at individual degrees of knee flexion with repeated measures ANOVA's combined with post-hoc Student-Newman-Keuls tests, with significance set at  $p = 0.05$ . The analyses will focus on relative variations in the kinematics and pressure measurements, with the pre-operative condition treated as the control for each knee, with the goal of each procedure to reduce lateral patellar shift and tilt without increasing the contact pressure.

Analyses will be performed for various combinations of tibial tuberosity position and depth of the trochlear groove. For each combination, the statistical analyses noted above will be performed to compare the influence of the various surgical procedures on patellar tracking and contact, with an emphasis on determining the limits at which each procedure becomes ineffective in reducing lateral tracking without overloading cartilage. In addition, for each procedure multivariable linear regression analyses will be performed to relate the anatomical parameters to the change in the output parameters.

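### Aim 3 promises anatomical ranges with no rise in contact pressure, but ties its limits to difference tests on 12 models, with no interval or threshold to support a no-rise statement

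*Combined protocol and SAP*

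**What the plan says.** Specific Aim 3 (Compare surgical options as a function of patellofemoral anatomy) states the deliverable: "Simulations performed while varying anatomy will establish ranges over which each surgical option limits patellar maltracking without elevating contact pressures".

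The Approach section, Aim 3: Compare surgical options, gives the method. Outputs of the simulated procedures "will be compared between the 12 models at individual degrees of knee flexion", using repeated measures ANOVA with post-hoc Student-Newman-Keuls tests at the 0.05 level. Each knee serves as its own pre-operative control, and "The analyses will focus on relative variations in the kinematics and pressure measurements". The same tests are repeated for each combination of tuberosity position and trochlear depth, "with an emphasis on determining the limits at which each procedure becomes ineffective in reducing lateral tracking without overloading cartilage". Separately, for each procedure, "multivariable linear regression analyses will be performed to relate the anatomical parameters to the change in the output parameters".

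The documents give no confidence interval, no margin or pressure cut-off, no minimum reduction in shift or tilt, and no rule for turning results at several flexion angles into one range. They also give no power statement and no SD. The error measures described under Aim 1 concern validation of the models against in vivo data, not this goal.

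**The concern.** A statement that pressure is not elevated is a claim of absence. The tests named in Aim 3 are built to detect a difference. When such a test is not significant, the rise may be absent, or it may be real and too small to detect with 12 knees. The test alone cannot separate the two.

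The same applies to the limits. If the edge of a range is placed where p crosses 0.05, its position depends on the number of models and on the spread between knees as well as on anatomy. The error can run either way. With variable changes, real rises go unflagged and ranges look too wide. With very uniform changes, trivial rises become significant and workable combinations are excluded.

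What is at stake is what the published ranges can claim, and these ranges are Aim 3's main product.

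**Working it through.** The plan contains no power calculation to reproduce. Its only figure is the number of models, 7 existing + 5 recruited = 12, which adds up. The cover letter says that only three of the five were enrolled and that other imaging made up the number, so n = 12 is used.

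**Inputs.** From Aim 3: n = 12, level 0.05, each knee compared with its own pre-operative state. Assumed: a two-sided test and normally distributed changes. Effects are in SDs of the within-knee pressure change, because no SD is given.

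**Step 1: chance of missing a true rise, one contrast at one angle.** A paired t-test has n − 1 = 11 df, critical value 2.201 and noncentrality d√n, with √12 = 3.464.

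| True rise d (SD) | Noncentrality | P(not significant) |
|---|---|---|
| 0.5 | 0.5 × 3.464 = 1.73 | 0.647 |
| 0.75 | 0.75 × 3.464 = 2.60 | 0.342 |
| 1.0 | 1.0 × 3.464 = 3.46 | 0.117 |

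A simulation of 100,000 runs gave 0.646 at 0.5 SD and 0.115 at 1.0 SD. A power of 80% needs a true rise of about 0.89 SD.

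**Step 2: what a non-significant result leaves open.** The 95% interval half-width is 2.201/3.464 = 0.635 SD. A result just short of significance has an upper limit of 2 × 0.635 = 1.27 SD.

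**Step 3: dependence on sample size.** The smallest observed change that reaches significance is t(0.975, n − 1)/√n.

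- n = 12: 2.201/3.464 = 0.64 SD
- n = 24: 2.069/4.899 = 0.42 SD
- n = 48: 2.012/6.928 = 0.29 SD

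With the same anatomy and the same true changes, a limit defined by significance would therefore sit in a different place.

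**Step 4: sensitivity to the paired simplification.** These cases rest on further assumptions that are not in the documents.

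- ANOVA followed by stepwise Student-Newman-Keuls, four conditions, sphericity, one angle: misses are about 78%, 43% and 14% at 0.5, 0.75 and 1.0 SD.
- A combination is excluded if any of five angles shows a significant rise (paired test, equal rise at every angle, between-angle correlation 0.5 to 0.9): misses fall to 29–49%, 6–20% and 1–5%.
- As above, but the rise is at only one of the five angles: misses return to 62–65%, 34% and 12%.

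The miss rate therefore depends strongly on the angle rule, which the plan does not state.

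**The case against.** The strongest reply is that the plan already estimates size of change. It emphasises relative change from each knee's own control and plans regressions of that change on anatomy. This stands. A reader might infer that nothing in the plan could support the Aim 3 result, and that would go too far: the regressions are the right raw material. What they lack is an interval and a value of change at which a limit is read.

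A reader might also infer that the plan treats p > 0.05 as proof of no rise. It does not say so. The miss rates show what would follow if limits were read that way. They do not measure an error the plan has committed.

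The SD objection also stands. Each model is compared with itself, so the SD is the spread of the change between knees. If that spread is small, 1 SD may be a trivial pressure difference. A stated size of change would still be needed to say so.

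It is tempting to add that the number of flexion angles is missing. The documents do not support this as a fault of the plan: the text under Aim 1 breaks off mid-sentence where the simulated squatting activity is introduced, and the angles may have stood there. The cover letter also calls the protocol an abbreviated grant application, so a cut-off may exist in the full one.

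Finally, this is exploratory modelling, and enrolled subjects are treated "with the procedure performed based solely on clinical evaluation". No participant's care turns on these ranges. That limits the severity but leaves the mismatch between method and conclusion.

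**Conclusion.** The concern holds as a mismatch between method and claim. Aim 3 promises ranges with no rise in pressure and ties the limits to repeated difference tests, and neither those tests nor the regressions as described carry an interval or threshold that would support a no-rise statement.

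For one paired contrast at one angle with 12 knees, a true rise of 0.5 SD is missed about 65% of the time and one of 1.0 SD about 12%. These figures assume a two-sided 0.05 test and normal changes, and they cannot be converted to pressure units because no SD is given. The dependence of a significance-based limit on n (0.64, 0.42 and 0.29 SD at 12, 24 and 48) needs no assumption about the true effect.

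This should be fixed before ranges are reported. No stated figure is wrong, and the planned simulations can stay as they are.

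**What to change.** 1. For each anatomy combination, report the mean within-knee change from the pre-operative condition in pressure, shift and tilt, with a 95% confidence interval.
2. Report the planned regressions with intervals that treat the knee as the unit, for example through a random knee effect. Where the interval for a limit spans the tested range, say that the limit is not located.
3. Base any no-rise statement on the upper confidence limit for pressure change, compared with a size of change that the investigators state and justify, labelled post hoc if outputs have been seen. It helps to show that value beside the model error already planned under Aim 1 ("The accuracy of computational simulation will be reported in terms of root mean square errors between the computational and in vivo data"). Otherwise drop the no-rise wording and report only that no significant rise was detected.
4. State how results across flexion angles combine into one range: one named summary per knee, or a requirement at every tested angle.

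Items 1, 2 and 4 are the minimum. A margin is needed only if the no-rise claim is kept.

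**Cost.** No new patients or simulations are needed. The work lies in justifying a threshold, for which the documents give no value. Some ranges will be narrower. With no true rise, 12 knees at one angle have an 80% chance of clearing a margin of about 0.89 SD using the upper end of a two-sided 95% interval, or about 0.77 SD using a one-sided 95% limit. Limits will also be imprecise. In one assumed linear case (anatomy scaled 0 to 1 in seven levels, tracking reduction 1.5(1 − x) SD, threshold 0.5 SD, within-knee correlation 0.5), the true limit is 1 − 0.5/1.5 = 0.67, and 95% of estimates from 12 knees fall between 0.38 and 0.98. The intervals make that imprecision visible.

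### Aim 3's anatomy regression has no repeated-measures structure although anatomy is varied within each of 12 knees; read naturally, its standard errors would be wrong, in a direction the documents do not settle

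*Combined protocol and SAP*

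**What the plan says.** The Approach section for Aim 1 sets the number of knees: "Models for dynamic simulation of knee function will be developed to represent 12 knees with recurrent patellar instability". Specific Aim 3 says that anatomy will be changed in these models: "Techniques to alter trochlear dysplasia and tuberosity lateralization will also be developed and applied to the models". The Approach section for Aim 3 repeats this: "Analyses will be performed for various combinations of tibial tuberosity position and depth of the trochlear groove".

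Two analyses follow in that section.

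- Repeated measures ANOVAs at individual flexion angles, "combined with post-hoc Student-Newman-Keuls tests, with significance set at" p = 0.05. They are rerun at each anatomical setting: "For each combination, the statistical analyses noted above will be performed to compare the influence of the various surgical procedures". Results are read relative to baseline, "with the pre-operative condition treated as the control for each knee".
- A regression, introduced as an addition: "for each procedure multivariable linear regression analyses will be performed to relate the anatomical parameters to the change in the output parameters".

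The repeated-measures wording is attached to the ANOVAs only. No section gives the regression a knee effect, a random effect, a clustered standard error, a unit of analysis or a significance level.

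**The concern.** The ANOVAs run separately for each anatomical combination, whereas the regression runs for each procedure. If the same anatomical levels are imposed on every knee, both predictors are constant within a combination, so a regression on them has to span combinations. Each knee then contributes as many rows as there are combinations.

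Rows from one knee are not independent. Taking the change from the knee's own pre-operative state removes its baseline level. It does not remove differences between knees in how much they respond to surgery, or in how steeply that response depends on anatomy. An ordinary linear regression on the pooled rows ignores both.

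At stake is the stated precision of the one analysis that directly estimates how anatomy relates to the change in output. A reader could not tell whether it rests on 12 knees or on, say, 12 × 9 = 108 rows (9 combinations being an assumption).

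**Working it through.** **Inputs from the documents.** 12 models, planned as 7 existing plus 5 recruited: 7 + 5 = 12. The plan gives no effect size, standard deviation, standard error or power for the regression, so there is no statistical figure to reproduce.

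**Assumed inputs, not in the documents.** Combinations per knee m = 9 (a 3 × 3 grid), with m = 25 (5 × 5) as a check. ICC, the share of change-score variance due to the knee apart from any slope differences, is 0.05, 0.3, 0.5 or 0.8. Two anatomical parameters are scaled to SD 1. Knee-intercept variance is ICC and residual variance is 1 − ICC. Slope variance on each parameter is a ratio times ICC. Tests are two-sided at 5% with no true effect.

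**Direction, by formula (identical levels in every knee).** With K knees, intercept variance A, slope variance T and residual variance E, the pooled slope has approximately

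- true variance = (mT + E) / (Km);
- variance reported by the pooled fit = (A + 2T + E) / (Km).

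These agree when A = (m − 2)T, that is, T/A = 1/(m − 2): 1/7 = 0.14 for m = 9 and 1/23 = 0.043 for m = 25. Below that ratio the reported standard error is too large; above it, too small.

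Reported over true standard error at m = 9, by formula:

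- Common slope (T = 0): 1/√(1 − ICC) = 1.03, 1.20, 1.41, 2.24. Simulation gave 1.02, 1.18, 1.39, 2.16.
- Slope variance equal to intercept variance (T = A): √[(1 + 2·ICC)/(1 + 8·ICC)] = 0.89, 0.69, 0.63, 0.59. Simulation gave 0.87, 0.67, 0.61, 0.58.

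**Size, by simulation.** Type I error of the pooled regression with no knee term, 12 knees, 9 combinations, 10,000 runs per cell:

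| Scenario | ICC 0.05 | 0.3 | 0.5 | 0.8 |
|---|---|---|---|---|
| Identical levels, common slope | 4.5% | 2.2% | 0.9% | 0.0% |
| Slope variance 10% of intercept variance | 5.2% | 4.3% | 4.2% | 4.0% |
| Slope variance 25% | 5.8% | 7.6% | 9.9% | 10.9% |
| Slope variance 100% | 8.6% | 18.6% | 23.4% | 25.2% |
| Native anatomy plus offset, native SD half the offset SD | 5.3% | 7.2% | 8.8% | 12.2% |
| Native anatomy plus offset, equal SD | 6.6% | 15.9% | 22.4% | 31.3% |

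With 25 combinations (6,000 runs) the same scenarios span 4.2% to 15.7% at ICC 0.05, and 0.0% to 54.0% at ICC 0.8.

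**Does the change score remove the problem?** At m = 9, raising the variance of the knees' baseline level from 0 to 4 left type I error almost unchanged: 5.3% against 4.7% with no response variance, and 19.0% against 18.5% with response variance 0.3 and slope ratio 1. The baseline cancels; the difference in response does not.

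**The alternative.** A one-sample t-test on the 12 per-knee slopes held 4.4% to 5.3% in every scenario. A knee intercept alone is not enough when slopes differ: with slope SD 0.5 and ICC 0.5, knee fixed effects gave 14% (4 rows per knee) and 26% (9 rows).

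**The case against.** The plan never says that rows are pooled. Multivariable linear regression does not rule out a knee term or one row per knee, and the cover letter calls the document an abbreviated grant application, so silence proves little. The same section recognises within-knee structure in its ANOVAs and in its use of each knee as its own control. Nor does any section say that common levels are imposed; if native values are kept, a one-row-per-knee regression is possible. This stands as a limit: pooling is the natural reading, not the only one.

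The error rates rest on assumed values, and on random residuals that a deterministic simulation would not produce in that form. Within-knee residuals there would be largely lack of fit, possibly shared across knees. The percentages therefore show what can happen and are not forecasts. The 12 knees are still a sample, so the clustering question remains.

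A reader might infer three stronger things, none of which the documents support:

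- That the regression is bound to give false positives. It can equally be conservative.
- That Aim 3's conclusions on anatomy fall with it. The ANOVAs at each combination, and the ranges and limits drawn from them, also address where each procedure stops working, and they are unaffected.
- That a stated error rate is breached. The 0.05 level belongs to the ANOVAs; the regression has none.

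**Conclusion.** The point holds as a minor one. As written, and on its natural reading, the regression treats repeated rows from 12 knees as independent, and nothing elsewhere in the documents corrects this. The standard error, interval and p-value are affected; on a balanced grid of common levels the slope estimate itself is not.

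The direction and size cannot be determined from the documents. With 9 combinations the assumed range is about 0% to 31% at nominal 5%. At ICC 0.05 it is 4.5% to 8.6%, so the matter is small if knees respond alike. If one row per knee is intended, the point falls away, but the text does not say so.

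**What to change.** State in the Approach section for Aim 3 that the knee is the independent unit in the regression. For anatomy varied within knees, use one of the following:

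- fit the regression within each knee and test the 12 slopes for each parameter with a one-sample t-test (12 − 1 = 11 df); or
- fit a linear mixed model with random knee intercept and random slopes on the anatomical parameters.

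If native anatomy is used as a predictor, analyse it separately with one row per knee (12 − 3 = 9 residual df with two predictors). Say which anatomical levels are imposed and whether they are common to all knees.

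This takes two or three sentences and a different model call on the same simulations, with no new models or subjects. The price is fewer degrees of freedom and wider intervals where knees differ. When correlation is low and slopes are common there is a small loss of power: with 9 combinations, 80% for the per-knee test against 85% pooled at ICC 0.05. At ICC 0.3, 0.5 and 0.8, with the slope again set for 80% on the per-knee test, the pooled fit has 77%, 62% and 17%, so there the per-knee test is the more powerful.

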### 2. Characterize influence of surgical stabilization on knee function for individual patients

The multibody dynamic models will be used to simulate MPFL reconstruction and tibial tuberosity medialization. MPFL reconstruction will be simulated with variations in the femoral attachment position, while the magnitude of tuberosity realignment will be varied. The actual surgical procedures performed on the patients will be simulated, with the influence on lateral tracking and contact patterns compared to in vivo results to validate simulation of the surgical procedures.

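### Aim 3 compares procedures across anatomy, but no planned analysis gives a confidence interval or test of how the difference between procedures changes with anatomy

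*Combined protocol and SAP*

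**What the plan says.** The title of the third Specific Aim is "Compare surgical options as a function of patellofemoral anatomy". Its text sets two tasks. One is comparative: "Variations in patellar tracking and contact pressure will be compared between MPFL reconstruction and tuberosity medialization". The other is separate for each procedure: "Simulations performed while varying anatomy will establish ranges over which each surgical option limits patellar maltracking without elevating contact pressures".

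The Approach section for Aim 3 plans two kinds of analysis:

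- **Between procedures.** Outputs are compared "at individual degrees of knee flexion with repeated measures ANOVA's combined with post-hoc Student-Newman-Keuls tests", at a 0.05 significance level. Anatomy enters by repetition: "For each combination, the statistical analyses noted above will be performed to compare the influence of the various surgical procedures". The stated focus is "an emphasis on determining the limits at which each procedure becomes ineffective in reducing lateral tracking without overloading cartilage".
- **Across anatomy.** "for each procedure multivariable linear regression analyses will be performed to relate the anatomical parameters to the change in the output parameters".

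The second Specific Aim adds that each procedure has several simulated versions: "MPFL reconstruction will be simulated with variations in the femoral attachment position, while the magnitude of tuberosity realignment will be varied". No confidence interval is mentioned anywhere in the document.

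**The concern.** A comparison of two procedures as a function of anatomy asks whether the gap between them widens, narrows or reverses as tuberosity position or groove depth changes. That is a procedure-by-anatomy effect. The ANOVA compares procedures but treats anatomy as a stratum. The regression models anatomy but handles one procedure at a time. Neither gives an interval or a test for the quantity that joins the two.

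Without that, a reader of the results has two informal routes. One is to subtract the fitted slopes, which gives an estimate with no statement of uncertainty. The other is to look at which combinations reach significance. A difference in significance between two combinations is not evidence that the procedure difference itself changed. At stake is any statement that one procedure gains or loses ground against the other in a given anatomy.

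**Working it through.** **Inputs from the documents.** There are 12 knee models, 7 existing plus 5 to be recruited: 7 + 5 = 12, which reproduces the stated number. The cover letter reports that three of the five were enrolled and that other pre-operative imaging completed the set, so 12 is kept. The significance level is 0.05 (taken as two-sided; the text does not say). The documents give no number of anatomy combinations, power, effect size, SD or correlation.

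**Step 1. Where procedure and anatomy enter.**

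| Planned analysis | Procedure | Anatomy | Interval or test of procedure by anatomy |
|---|---|---|---|
| ANOVA with Student-Newman-Keuls | factor | stratum | none |
| Multivariable regression | stratum | predictor | none |

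**Step 2. What subtraction gives.** Let b_M and b_T be the fitted slopes on one anatomical parameter for the MPFL and tuberosity procedures. On a common grid, b_M − b_T equals the mean over knees of the within-knee slope differences (a numerical check agreed to 1e-15). The point estimate is therefore recoverable. Its variance is Var(b_M) + Var(b_T) − 2 Cov(b_M, b_T). Both slopes come from the same 12 knees, so the covariance is not zero in general, and separate regressions do not supply it.

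**Step 3. What the significance pattern would show if it were used.** Assume that the true procedure difference is identical at every combination. For knee k and combination c, write the within-knee difference as D_kc = δ + √ρ·u_k + √(1−ρ)·e_kc, with u and e standard normal. Choose δ to give the assumed power for a paired t-test in 12 knees: δ = 0.620 SD for 50% and 0.889 SD for 80%. Count the studies in which some combinations are significant and others are not.

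| Power per combination; correlation ρ | 4 combinations | 9 | 16 |
|---|---|---|---|
| 50-80%; 0.3-0.7 | 33-75% | 48-93% | 57-98% |
| 80%; 0.9 | about 20% | 29% | 34% |
| 90%; 0.9 | about 12% | 18% | 22% |
| 95%; 0.9 | about 7% | 11% | 13% |

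Over 50-95% power and correlation 0.3-0.9, the range is about 7% to 98%. Replacing the paired t-test by repeated measures ANOVA followed by Student-Newman-Keuls, with 3 or 5 conditions, changes the first row little: 33-72%, 46-93% and 54-98%.

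With only two anatomy settings, 50% or 80% power and correlation 0 to 0.8, separate tests disagree in 15-50% of studies. A direct test of the change in the difference is falsely positive in about 5% throughout.

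**Step 4. Precision of a direct estimate.** Take one slope difference per knee, 12 knees, 11 df.

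- 95% CI half-width: t(0.975; 11)/√12 = 2.201/3.464 = 0.635 SD of the slope difference.
- Detectable at 80% power (noncentral t, noncentrality Δ√12): Δ = 0.889 SD.

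**The case against.** The strongest reply is that the main product of Aim 3 is separate for each procedure. Both the ranges in the Specific Aims and the limits in the Approach ask where a given procedure stops working relative to that knee's pre-operative state. Those questions need no interaction test, and the per-combination ANOVAs address them. MPFL reconstruction and medialization are also compared at every combination, which is one fair reading of comparing options as a function of anatomy. All this stands, and it confines the gap to the comparative half of the aim.

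Second, the planned regressions already contain the point estimate. This also stands: what is missing is its uncertainty.

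Third, the documents nowhere say that the pattern of significant combinations will be read as an anatomy effect. A reader might infer that they do, since significance is the only stated criterion, but the text does not support it. The simulated percentages therefore describe a misreading that the plan leaves open, not one that it prescribes. They also fall at high power and high correlation. Repeated simulations of the same knees could well be highly correlated, and at 99% power with correlation 0.7 the figures are only 3%, 5% and 7%.

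Fourth, the document is an abbreviated grant application and enrollment has ended. A fuller text might say more, but nothing supplied fills the gap, and the remedy needs no patients.

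**Conclusion.** The concern holds in a limited form. The plan compares procedures within each anatomy combination and relates each procedure's effect to anatomy, so it would be wrong to say that it makes no comparison or ignores anatomy. It lacks an interval or test for how the between-procedure difference changes with anatomy. That gap follows from the text alone and needs no assumption.

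The size of the consequence does rest on assumptions. If significance patterns stood in for the missing estimate, misleading mixed patterns would occur in about 7-98% of studies under the ranges in the working. The width of that range means that the documents do not fix how often this would happen. The 0.64 SD half-width and the 0.89 SD detectable difference depend only on 12 knees, the 5% level and approximate normality.

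A reader might also infer that the regressions pool all simulations as independent rows and so give wrong error rates. The text does not define a regression row, and one row per knee would have no clustering problem. That reading is unsupported and is not a ground for this point.

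**What to change.** In the Approach section for Aim 3, add a within-knee analysis of the procedure-by-anatomy effect for each main output (lateral shift, tilt, contact pressure) at the flexion angles already analysed:

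1. Name which simulated version represents each procedure.
2. For each knee, estimate the between-procedure difference in slope on tuberosity position and on groove depth.
3. Report the mean over the 12 knees with a 95% t-based confidence interval (11 df). A mixed model with knee-level random effects and procedure-by-anatomy terms would be equivalent.
4. State that this estimate, not the pattern of significant combinations, answers whether anatomy changes the procedure comparison.
5. Keep the per-combination ANOVAs for the per-procedure limits.
6. Label the analysis post hoc if results have already been seen.

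The cost is some wording and modest extra analysis. No patients or scans are needed, and no further simulations if every procedure is run at every combination in every knee, as the per-combination ANOVAs already require.

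There are three downsides. Precision is low with 12 knees. A straight-line slope may miss a threshold and does not itself give the limits. Two anatomical parameters, several outputs and several flexion angles make many tests, so the intervals rather than the p values should carry the message.
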